## 1.0 Objectives

### 1.1 Study Objectives

The purpose of this study is to evaluate the role of single dose 4-aminopyridine (4-AP) on the diagnosis of severing vs non-severing nerve injury after peripheral nerve traction and/or crush injury. The investigational treatment will be used to test the hypothesis that 4-aminopyridine can speed the determination of nerve continuity after peripheral nerve traction and/or crush injuries allowing the identification of incomplete injuries earlier than standard electrodiagnostic (EDX) and clinical assessment.

### 1.2 Primary Study Endpoints

Primary Aim and Study Endpoint: Return of voluntary function and subjective sensation not present after trauma.

**Summary of Specific Aims:** This proposal contains two distinct aims to be investigated in two similar but distinct groups of patients. This will be measured by sensory, motor and sudomotor (electrical conduction tests), and electrodiagnositc (EDX) testing.

**Aim 1:** To examine the mechanistic effect of 4AP on the return of sensorimotor function and EDX sensitivity in the setting of nerve dysfunction from orthopaedic trauma. This aim tests the hypothesis that oral one-time administration of 4AP provides transient return of function and EDX sensitivity to the traumatically denervated limb in alert patients with known limb injuries not involving the central nervous system.

**Aim 2:** To examine the mechanistic effect of 4AP on the return of sensorimotor function and EDX sensitivity in the setting of iatrogenic nerve injury after surgical intervention. This aim tests the identical hypothesis as in Aim 1 in a distinct group of patients, whose nerve dysfunction is the result of a clinical intervention, and whose function before that intervention was intact.

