# **3.0 Inclusion and Exclusion Criteria**

## **3.1 Inclusion Criteria**

- Patients with trauma involving two or less limbs where the continuity of a given peripheral nerve or nerves is unclear on presenting physical examination.
- Closed soft tissue envelope obscuring direct observation of the continuity of the affected nerve.
- Cognitive ability to report sensory and motor deficit during examination.
- Able to complete single day dosing within seven days (168 hours) of nerve injury diagnosis.
- Eligible for standard of care plan of monitoring vs surgical exploration of the nerve.
- Adults subject aged 18-90
- Known limb trauma which resulted in nerve injury (aim 1) or post-operative/post intervention nerve injury (aim 2).
- Ability to give written informed consent.
- Capable of safely undergoing electrodiagnostic testing (EDX).
- Availability for all testing days and main trial day.

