**EDX testing:** Patients enrolled in the trial will undergo serial EDX testing by a trained member of the study team to specifically assess the continuity of the injured limb nerves. For patients with known single-nerve lesions below the plexus trunk level, the testing will include nerve conduction studies (NCS) and electromyography (EMG). The NCS will include one sensory and one motor nerve (if indicated) with needle exam of two muscles supplied by the motor nerve. EMG will show motor units which will allow for assessment of their size and recruitment, and the presence or absence of active denervation (fibrillation potentials and positive sharp waves) depending on the timeline. It should be noted that our early testing phase is within four days of injury and that these findings of chronic denervation should only be present at 6 and 12 week testing. The NCS will be assessed for latencies, amplitudes, and conduction velocities values. Of particular note is the natural difficulties with the use of EDX in this setting. The presence of non-recordable or absent responses on NCS can be interpreted as abnormal or inconclusive depending on multiple factors including technical limitations. The presence of active denervation and motor unit size and recruitment abnormalities are time-dependent. These do not usually manifest prior to 10-14 days. As such, we expect most of these studies to be inconclusive on the trial day. If, the nerve is believed to be continuous by this test, then the result will be saved and sealed for analysis post-hoc. This test will be performed at baseline before challenge with 4AP or placebo and then hourly for five hours after challenge. There will therefore be a total of six tests performed over the course of the testing day (Figure 1, blue arrows with the 5th post-test being done in conjunction with the Return to Baseline test). Clear indications of continuity will be shared with the main study coordinator at the end of the day and the patient will be informed of the result of the EDX test at the conclusion of the day (but not which group their allocation).

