## 7.2. 1 Visit 1 in Clinical Research Center (CRC) and/or Inpatient setting~8 hours

**Trial Logistics and Organizing framework:** Patients for this trial are divided into two aims. Patients enrolled for one aim, are excluded from the other aim, because the causes of the injury, which define the aim, are exclusive. Aim 1 is for post traumatic neuropathy. Aim 2 is for post surgical or post intervention neuropathy. Within each aim, there are treated patients and placebo patients. Only one patient will be evaluated at a time. Evaluation takes one day. Patients will be randomized in the Penn State University Clinical Research Center (CRC) or at the bedside, where they will stay for a period of analysis afterwards that lasts a few hours.

[figure not shown]
Eligible, consented patients will present for testing from one of three locations (emergency department, inpatient ward, or home). Patients will undergo testing in the CRC and/or bedside under the direction of trial personnel. Testing will be initiated by patients undergoing a thorough sensory and motor evaluation and establishing an intravenous line for blood sampling. A baseline blood sample and EDX study (prior to drug or placebo) and sensorimotor examination will be performed. These tests comprise part of a standardized array of tests performed hourly. This array of tests (serum 4AP level, EDX study, and sensorimotor examination) will be repeated every hour after treatment for five hours (Figure 1) during which the drug will have decreased to a level low enough to have no expected effect. The final hourly test is the return to baseline test. It is likely going to occur at the fifth hourly posttest, but is depicted separately for clarity. Only five tests after dosing will be necessary, based on our expectations from known pharmacokinetic data.

Finally, testing is concluded at the end of this period. Research subjects will be provided a diary and asked to record symptoms as instructed. The subjects will be asked to maintain the diary for 20 weeks and the diaries will be reviewed at each follow up visit and collected at or after the final 20 week visit.

[figure not shown]

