### **8.3 Statistical methods**

Consultation with the biostatistical team included separate discussions with [name] and [name]. This trial is a pilot study in preparation for an NIH funded randomized controlled trial which is currently in preparation.

Our methods will be to stratify nerve injuries based on injury severity and compare placebo to drug patients using the methods listed below:

This proposal contains two distinct aims to be investigated in two similar groups of patients.

**Aim 1:** To examine the effect of 4AP on the return of sensorimotor function and EDX sensitivity in the setting of nerve dysfunction from orthopaedic trauma. This aim tests the hypothesis that oral one-time administration of 4AP provides transient return of function and EDX sensitivity to the traumatically denervated limb in alert patients with known limb injuries not involving the central nervous system.

**Aim 2:** To examine the effect of 4AP on the return of sensorimotor function and EDX sensitivity in the setting of iatrogenic nerve injury after surgical intervention. This aim tests the identical hypothesis as in Aim 1 in a distinct group of patients, whose nerve dysfunction is the result of a clinical intervention, and whose function before that intervention was intact.

Statistical planning was performed in the design of this trial with a qualified biostatistician, who also sits on the Data Safety Monitoring Board for this study. Statistical methods will be used to evaluate both the effect of treatment as well the effects of injury type (either aim 1 or aim 2). Groups will be analyzed separately within each aim.

Categorical variables (as in the presence or absence of sensation) will be compared (between treated and untreated groups for each aim) using Chi-squared testing. Continuous data (as in nerve conduction velocity from EDX) will be compared with standard student's T testing. Grouped data variables will be first compared in linear models (accounting for mixed effects of multiple variables as indicated). Formal recommendations for the statistical methods to be used for posthoc comparisons will be made by the biostatistician designee of the DSMB ([name]), who has aided in the planning of this trial and is a non-conflicted member of the trial team.

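### The primary endpoint and its between-arm test are not tied to the same-day pre-dose examination, so recovery before dosing can be scored as a response in either arm

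*Combined protocol and SAP*

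**What the plan says.** All references are to the combined protocol and SAP.

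- **Endpoint.** Section 1.2 defines it as "Return of voluntary function and subjective sensation not present after trauma". It gives no assessment time, no threshold and no pre-dose reference. Section 1.3 lists no secondary endpoint.
- **Hypothesis.** The same section states that "oral one-time administration of 4AP provides transient return of function and EDX sensitivity", which is a change around the dose.
- **Eligibility and timing.** Section 3.1 admits patients "where the continuity of a given peripheral nerve or nerves is unclear on presenting physical examination" who are "Able to complete single day dosing within seven days (168 hours) of nerve injury diagnosis". Section 15.2 requires a loss that the patient can appreciate at enrollment. No section asks for the deficit to be confirmed again just before dosing.
- **Trial-day tests.** Section 7.2.1 says "A baseline blood sample and EDX study (prior to drug or placebo) and sensorimotor examination will be performed". The EDX paragraph of 7.2 says "This test will be performed at baseline before challenge with 4AP or placebo and then hourly for five hours after challenge".
- **Analysis.** Section 8.3: "Categorical variables (as in the presence or absence of sensation) will be compared (between treated and untreated groups for each aim) using Chi-squared testing". No baseline term or change rule is given. The biostatistician's text in 8.3 describes testing before and after administration and a mixed-effects logit model, but does not define a responder.

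**The concern.** The drug is expected to restore function for a few hours, so the relevant reference is the state just before the capsule is taken. The written reference is the state after trauma, which may be days older.

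Take a patient who is numb at presentation and at enrollment, regains feeling while waiting, and is then dosed. Read literally, that patient meets the endpoint whichever capsule was given, and is counted as having sensation in the chi-squared table. Nerves in continuity can recover unaided, and these are the nerves the trial wants to identify.

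Two things are at stake. The first is a smaller drug-placebo difference in a small study. The second is an inflated placebo return rate in a pilot whose stated purpose (8.1 to 8.3) is to supply preliminary data for a larger trial. Section 19.1.2 also plans an O'Brien-Fleming look at about 13 patients per aim, which needs an unambiguous responder.

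**Working it through.** **What the documents supply.** The wait is at most 168 / 24 = 7 days from diagnosis. Section 3.3.2 gives 25 to 34 patients per aim, and 2 × 25 = 50 matches the target in 8.1. No alpha, power, response rate, allocation ratio or spontaneous recovery rate is stated, so there is no planned figure to reproduce.

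**Assumptions for illustration.** 25 patients in one aim, split 13 drug and 12 placebo. Among patients still without function at dosing, true return is p = 0.60 on drug and 0.10 on placebo. A fraction f, equal in both arms, has regained the scored function before dosing and keeps it through the tests. f runs from 0 to 0.3. Tests are two-sided at 0.05, with power by exact enumeration of two binomials.

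**Literal endpoint.** Observed rate = f + (1 − f)p. For f = 0.3: drug 0.3 + 0.7 × 0.60 = 0.72; placebo 0.3 + 0.7 × 0.10 = 0.37.

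| f | Drug | Placebo | Difference | Power, uncorrected chi-squared | Power, Fisher |
|---|---|---|---|---|---|
| 0 | 60% | 10% | 50 points | 79% | 73% |
| 0.1 | 64% | 19% | 45 points | 63% | 61% |
| 0.2 | 68% | 28% | 40 points | 52% | 51% |
| 0.3 | 72% | 37% | 35 points | 42% | 41% |

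**Pre-dose responder, everyone randomised kept, recovered patients counted as non-responders.** Observed rate = (1 − f)p.

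| f | Drug | Placebo | Difference | Power, uncorrected chi-squared | Power, Fisher |
|---|---|---|---|---|---|
| 0.1 | 54% | 9% | 45 points | 72% | 63% |
| 0.2 | 48% | 8% | 40 points | 65% | 53% |
| 0.3 | 42% | 7% | 35 points | 57% | 42% |

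The absolute difference is (1 − f) × 50 points in both tables. Rewording alone therefore removes the inflation of the placebo rate but does not restore the difference, because recovered patients cannot respond. It regains part of the chi-squared power and almost none of the Fisher power.

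**Pre-dose responder, recovered patients not randomised.** The rates stay at 60% and 10%. Consented patients needed per 25 randomised = 25 / (1 − f): about 28, 31 and 36 for f = 0.1, 0.2 and 0.3.

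**Other assumed rates.** With 50% versus 5% and 13 versus 12, literal chi-squared power falls from 79% to 34% over the same range, and the difference from 45 to 31.5 points.

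**Direction.** With no drug effect (5% true return in both arms), chi-squared type I error is 0.3%, 3.5%, 5.3% and 5.0% for f = 0, 0.1, 0.2 and 0.3. There is no material inflation.

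**The case against.** The strongest reply is that a pre-dose reading is already available. The pre-dose examination is itself after trauma, so the endpoint's words do not fix an earlier time. The hypothesis speaks of transient return. Section 7.2.1 and the Figure 1 legend plan a return-to-baseline test before discharge, 15.2 expects the return to be fleeting, and the biostatistician's text describes testing before and after. All of this stands: a careful analyst could adopt that reading. But neither the endpoint nor the 8.3 comparison requires it, and the sole primary outcome should not rest on that choice. The before-and-after text also says every patient receives both treatments, which conflicts with the parallel design in 7.1 and the Figure 1 legend, so it cannot settle the matter.

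The length of the wait is also uncertain. The EDX paragraph says "our early testing phase is within four days of injury", section 3.1 counts seven days from diagnosis, and 15.2 counts seven days from injury. A shorter wait leaves less room for recovery, so f may be small.

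Finally, this is a pilot with no power claim, and the baseline data are already collected. That limits the severity.

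A reader might go further in three ways that the documents do not support:

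- That the result would be biased toward drug. Pre-dose recovery falls equally on both arms in expectation, so the effect is dilution.
- That pre-dose recovery is certain to be counted. The text is open to both readings.
- That patients whose pre-dose EDX suggests continuity should be screened out. Section 7.2 seals such a result for post-hoc analysis and expects most trial-day studies to be inconclusive, and the Figure 1 legend uses EDX as a control.

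**Conclusion.** The concern holds as a gap between the endpoint and a baseline that the trial already measures. Applied as written, 1.2 and 8.3 can score pre-dose recovery as a response in either arm. Under the assumed 60% and 10%, 13 versus 12, and f from 0 to 0.3, the observed difference falls from 50 to 35 points and the placebo rate rises from 10% to 37%. The rates, the split and f are all assumptions. If f is near zero, the effect is negligible.

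The more durable harm is the inflated placebo rate carried into the next trial, since a pre-dose definition removes it at any f. Severity: should fix.

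**What to change.** 1. **Section 1.2.** Define a responder, per modality in the affected nerve's territory, as function absent at the same-day pre-dose test and present at one or more post-dose hourly tests.
2. **Section 8.3.** Apply the between-arm comparison to that variable.
3. **Section 7.2.1.** Complete the pre-dose sensorimotor examination before randomisation. Do not randomise patients whose scored deficit has fully resolved, and report how many there were.
4. **EDX.** Do not screen on the pre-dose EDX. Report the baseline result alongside the outcome.
5. **Passages to reconcile.** Section 3.2 excludes patients who cannot show motor control in the affected limb at baseline, which must be squared with a motor responder defined as absent at baseline. Also reconcile the crossover wording in 8.3 with the parallel design, and the differing statements of the testing window.

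**Cost.** No new tests are needed. Randomisation moves to after the examination, and some consented patients become screen failures: about 28 to 36 consented per 25 randomised if f is 0.1 to 0.3. If the team prefers to randomise such patients and count them as non-responders, the placebo rate is no longer inflated but only part of the power returns, as shown above.

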The many trials on 4-AP have been conducted using both immediate release 4-AP and sustained release 4-AP. The difference between the immediate release and sustained release formulations are that the sustained release formulation helps to decrease the peaks and troughs in serum levels that can occur with larger doses of immediate release formulations.

In respect to the use of *immediate release* formulations of 4AP (not proposed for use in this study but relevant for evaluation of safety), the following studies on multiple sclerosis patients are the most pertinent:

1. 4-Aminopyridine in patients with multiple sclerosis: dosage and serum level related to efficacy and safety. Van Diemen HA, Polman CH, Koetsier JC, Van Loenen AC, Nauta JJ, Bertelsmann FW. Clin Neuropharmacol. 1993 Jun;16(3):195-204.

In these studies, nonenteric-coated capsules containing 4-AP or placebo were administered orally for 12 weeks, the starting dosage was 10-20 mg orally per day in 2-3 divided doses. The daily dosage was elevated with 5-15 mg at week two and week six. Blood samples, to determine serum levels at the end of the first and second oral treatment, were taken 1.5-2.5 hours after the latest intake of medication.

Side effects were minimal in these studies and mostly were confined to paresthesias and/or dizziness/lightheadedness and nausea/vomiting and were not considered to be significant by the patients.

The mean dosage given to patients was 31.2 mg per day and ranged from 10-50 mg per day. Thus, the average dose was higher than we have proposed.

Capsules were divided in 2-4 doses and ranged from 0.17- 0.55 mg/ kg. On average, 4AP serum levels increased 1.3 ng/ml per mg 4- AP/day. Side effects were less frequent with oral dosing than with intravenous dosing. When side effects occurred, they mostly occurred within 30-45 minutes after taking the medication and generally resolved within 2-5 hours, with half the patients not experiencing any side effects.

The rapid resolution of side effects with orally administered 4-AP in an immediate release formulation was very favorable.

One patient, who received three oral doses daily at twice the concentration that are proposed (i.e., 10mg per capsule instead of 5 mg/capsule), was closely studied at multiple time intervals in this very early study. Following an initial rapid climb in serum levels to 114 ng/ml, subsequent doses caused increases to lower levels of 60 ng/mL or 80 ng/ml.

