**Sensory functional testing:** The most complete set of clinical examination tests must be employed to achieve our aims at understanding the mechanism of 4AP mediated return of function (or lack thereof). Each nerve in the body contains an expected sensory nerve dermatomal distribution on the skin. Sensory testing of this distribution is performed to test every type of fiber in the sensory portion of the nerve including: Semmes-Weinstein monofilament responses; static and moving two-point discrimination; light-touch sensation (a commonly used subjective assessment used in trauma patients); and subjective reports of sensation both inside and outside the dermatome. These reports will be scored to reflect 2:1 weight of objective (e.g., monofilament) over subjective (e.g. reported sensation, light touch sensation), according to the same protocols used previously. In the hand, individual sides of each finger (e.g., for ulnar, median, and radial nerve distributions) will be tested as in our previous work. Patients will also be objectively graded on the withdrawal from a pin-prick using a sterile needle 27-gauge needle in the nerve distribution which is absent (8 pricks per patient). Patients will also have any relevant (well established) deep-tendon reflexes measured, although these are not available for every possible affected nerve, in contrast with the rest of the tests we employ.

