## **11.0 Potential Benefits to Subjects and Others**

### **11.1 Potential Benefits to Subjects**

A known risk in nerve injury is a delay in recovery of function attributable to inability to correctly diagnose a nerve laceration without EDX, which only becomes sensitive to the continuity of the nerve weeks after the injury. It is well known that early surgical exploration and repair of lacerations of the nerve is best in patients with known nerve lacerations and detrimental for patients found at surgery to have an unsevered nerve. As this trial offers no change in the overall standard of care for nerve patients other than a trial of a drug to see if it returns function or sensation (clear indications that the nerve is not severed), this trial does not alter the standard of care for these patients. The benefits are a clear indication of the status of the nerve weeks before the gold standard test can reveal the same information – but this benefit is only realized in the drug group and only if return of function is demonstrated. 4-AP is a known neuro-enhancing agent we hypothesize will potentially return function transiently but long enough to reveal those patients whose nerves are intact but not working. Furthermore, we predict this diagnostic intervention will also limit the difficulty and stigma associated with not knowing if their nerve has been cut, again a direct benefit only realized when continuity is demonstrated. This trial only affects patient decisions to pursue further treatment if return of function is clearly demonstrated. Otherwise, patients might have no return of function either because their nerve was indeed severed in the trauma or if they received placebo. As such, no direct conclusions or alterations in patient care will be based on these results for trial patients. Also, since there are additional research visits included at two week intervals in this trial, recovery will be followed with greater accuracy over time.

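### Spontaneous drug-induced tingling can be counted as return of subjective sensation, because the plan never says the sensation must be evoked by a stimulus and lie in the injured nerve's territory

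*Combined protocol and SAP*

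**What the plan says.** Section 1.2 gives the primary endpoint as "Return of voluntary function and subjective sensation not present after trauma". It sets no threshold, no time point among the hourly tests, and no rule for combining the motor and sensory parts.

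Section 7.2 (Testing, sensory functional testing) lists monofilament, two-point discrimination, light touch and pin-prick in the affected distribution. It also scores "subjective reports of sensation both inside and outside the dermatome". Objective items are weighted 2:1 over subjective ones.

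Section 8.3 says "Categorical variables (as in the presence or absence of sensation) will be compared" between treated and untreated groups within each aim, by chi-squared. Section 11.1 describes giving the drug "to see if it returns function or sensation (clear indications that the nerve is not severed"; the word there is *or*, so sensation alone is enough for that reading.

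On side effects, the first multiple sclerosis study summarised in 2.2 reports that they "mostly were confined to paresthesias and/or dizziness/lightheadedness and nausea/vomiting". They began mostly 30 to 45 minutes after intake and "generally resolved within 2-5 hours, with half the patients not experiencing any side effects". The doses behind this were immediate release: "The mean dosage given to patients was 31.2 mg per day and ranged from 10-50 mg per day".

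The trial gives one 10 mg extended-release tablet or a methylcellulose capsule (7.4.1), then repeats the test array hourly for five hours (7.2.1).

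**The concern.** A patient who feels new tingling after the capsule may report that feeling has come back. The plan gives the rater no rule for telling a spontaneous sensation with a systemic cause from one evoked by touching skin supplied by the injured nerve. Because methylcellulose would not cause drug paraesthesia, the miscounting would run in one direction. Randomisation does not remove a side effect that differs by arm. Blinding may be weakened by it, since a patient who notices tingling can guess the allocation while subjective items are being scored.

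The trial exists to distinguish severed from non-severed nerves (1.1). If tingling were scored as return in a patient whose nerve is severed, that would be the error the test is meant to avoid. Section 12.0 also leaves patients free to use their own subjective assessment in treatment decisions, so a misreading need not stay inside the dataset.

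**Working it through.** **Is there a rule that closes the gap?** Each candidate safeguard, compared with what would be needed:

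- *2:1 weighting (7.2).* It dilutes a subjective report within a score. It does not govern the presence/absence test in 8.3.
- *Evoked tests (7.2).* They are planned in the right territory, but none is a condition for counting subjective sensation as returned.
- *Reports from outside the dermatome (7.2).* They are collected and scored. No negative-control use is stated.
- *Dual independent assessment (19.1.2, Data Management and Monitoring).* It improves agreement on what the patient said. It does not address where the sensation came from.
- *EDX on the trial day (7.2).* The protocol expects most of these studies to be inconclusive.
- *Adverse event reporting (9.1).* New symptoms are logged as events. They are not removed from the endpoint. The risk list in 10.0 does not mention paraesthesia.

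**How much could it matter?** The plan has no figure to reproduce: 8.2 declines a sample size calculation, and no alpha, power or expected response rate is stated. What follows is an illustration.

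*Inputs.* 25 to 34 patients per aim (3.3.2). The total of 50 in 8.1 equals 2 × 25. Allocation ratio is not stated; 1:1 is assumed, so 13 v 12. Placebo report rate p0 = 5%, assumed. Share f of drug patients whose paraesthesia is scored as sensation, assumed. In the study cited, about half had no side effect, so f could not exceed about 50% there. Two-sided 5% level, assumed. No true drug effect.

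*Drug-arm rate.* pD = p0 + (1 − p0) × f. With p0 = 0.05:
- f = 5%: 0.05 + 0.95 × 0.05 = 0.0975
- f = 10%: 0.05 + 0.95 × 0.10 = 0.145
- f = 20%: 0.05 + 0.95 × 0.20 = 0.24
- f = 30%: 0.05 + 0.95 × 0.30 = 0.335

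*Test.* With a of n1 drug and b of n2 placebo patients reporting sensation, N = n1 + n2 and t = a + b, X² = N[a(n2 − b) − b(n1 − a)]² / [n1 n2 t (N − t)], significant if above 3.841. For 4 of 13 v 0 of 12, X² = 25 × 48² / (13 × 12 × 4 × 21) = 57,600 / 13,104 = 4.40. For 3 of 13 v 0 of 12 it is 25 × 36² / (13 × 12 × 3 × 22) = 32,400 / 10,296 = 3.15. So four reports on drug and none on placebo are enough; Fisher's exact test needs five.

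*False positive rate.* Sum the binomial probabilities over every significant table, Bin(13, pD) × Bin(12, p0):

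| f | Chi-squared | Fisher |
|---|---|---|
| 0% | 0.3% | 0.1% |
| 5% | 1.8% | 0.4% |
| 10% | 6.0% | 1.7% |
| 20% | 23.0% | 10.5% |
| 30% | 45.6% | 28.5% |

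*Sensitivity, chi-squared, f = 5/10/20/30%.* With p0 = 10% at 13 v 12: 3.7/7.5/19.7/36.1%. With p0 = 5% at 17 v 17 (34 per aim): 3.5/10.5/33.8/59.4%.

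The test is very conservative when f = 0, so at 13 v 12 the rate passes the nominal 5% only at f of roughly 10% or more.

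**The case against.** **The endpoint says *and*.** Tingling cannot move a muscle. If both parts must return, paraesthesia alone makes no responder. This stands as a limit: the figures above apply to the sensation comparison in 8.3, not to a conjunctive responder rule. But the plan states no such rule, 11.1 uses *or*, and 8.3 tests sensation in its own right.

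**The side-effect evidence is thin for this dose.** Paraesthesia is named in only one of the eight study summaries in 2.2, under repeated immediate-release dosing at a mean of 31.2 mg per day. Section 2.2 also says sustained release reduces peaks in serum level, and its single-dose summaries report no serious or bothersome effects up to 25 mg, and mild to moderate effects lasting no more than 60 to 90 minutes at up to 15 mg. This stands too. The rate, the body site and the timing after one 10 mg extended-release tablet are unknown, and the overlap of the 2 to 5 hour resolution with the five-hour test period is carried over from a different formulation.

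**Most of a sound definition is already in the battery.** The planned stimuli are evoked and territory-specific, and there is a pre-dose baseline. True; what is missing is the rule that makes them the criterion.

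**Stronger readings.** A reader might infer that the drug arm will produce false findings of continuity, or that the trial could not tell conduction from a side effect. The documents do not support either. No body site is given that would place tingling in the denervated territory, and EDX at 6, 12 and 18 weeks, or surgical exploration where it happens (7.2.2), can check continuity later. Nor would tingling mean that no nerve is conducting; it may arise in intact nerves. The point is only that the injured nerve need not be.

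**Conclusion.** The concern holds as a gap in the definition of returned sensation. As written, 1.2 and 8.3 allow spontaneous drug-induced paraesthesia to be counted, the placebo is inert, and any such error therefore favours the drug arm.

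Its size is not known. It is minor if about 5% of drug patients are miscounted (a false positive rate near 2% at 13 v 12) and serious at 20 to 30% (23 to 46% by chi-squared, 11 to 28% by Fisher). These figures rest on an assumed miscounting rate, an assumed 5% placebo response, 1:1 allocation, a two-sided 5% level and a sensation-only comparison. The finding itself rests on the text, not on those rates: nothing now in the plan would measure the miscounting or separate it from true return, and if the reports are not distinguished when taken they cannot be separated afterwards.

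**What to change.** In 1.2, 7.2 and 8.3, count return of sensation only when it is:

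- evoked by a stimulus already planned (monofilament, two-point discrimination, light touch or pin-prick);
- correctly reported by the patient;
- localised to the injured nerve's territory; and
- absent at the pre-dose test.

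Preferably add a few no-stimulus trials to each hourly sensory test, so that false reports can be counted in both arms. Record spontaneous tingling in its own field and do not count it as return. Use the reports from outside the dermatome, already collected, as a negative control for a systemic drug effect and not as evidence of return. Run the presence/absence comparison in 8.3 on this definition, and say in 1.2 whether the endpoint needs motor return, sensory return or both.

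The cost is protocol wording, a change to the case report form and a few blank stimuli per test. The downside is that some genuine spontaneous return of feeling will not be counted.
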